3. Subjects with any clinically significant abnormalities as determined by medical history, physical exam, clinical and lab evaluation suggestive of an underlying disease state that may, in the opinion of the investigator, confound the results of study, increase risk to the subject, or lead to difficulty complying with the protocol.
4. Subjects on chlorpromazine, PDE-5 inhibitors, nitrites and any medication with CNS effects with the exception of antipsychotic drugs (other than chlorpromazine) anticholinergics, b-adrenergic antagonists, amantadine, biperiden, diphenhydramine, lorazepam, zolpidem, and temazepam.
5. Medications which in the opinion of the PI, and in conjunction with the medical monitor, may be expected to significantly interfere with the metabolism or excretion of sodium nitroprusside, and/or may be associated with a significant drug interaction with sodium nitroprusside that may pose a significant risk to subjects' health and/or confound the study data.
6. Pregnant or breast-feeding patients. Women of childbearing potential must have a negative pregnancy test performed at screening visit prior to randomization and prior to baseline at visits 3 and 6. Women enrolled in this trial must use adequate birth control.
7. Subjects with a current (within the last 3 months) DSM-IV-TR diagnosis of alcohol or substance use disorder or dependence (excluding nicotine) as established by the clinical assessment (SCID) at the screening visit will be excluded.
8. Has tested positive for any of the following: cannabis, opioids, cocaine, amphetamines, barbiturates methadone, methamphetamine and phencyclidine at the screening or baseline visits. If positive, the urine drug toxicology screen may be repeated once based on investigator judgment, but due to safety concerns, the result must be negative for the subject to continue in the study.

9. Subjects at imminent risk of suicide or injury to self or others, as per the opinion of the investigator, or history of significant suicide attempt within the last 6 months as per C-SSRS.
10. Subjects that have taken an investigational drug or taken part in a clinical trial within 30 days prior to screening.
11. Any other reason that, in the opinion of the investigator, would compromise patient safety or integrity of the study

Table 1- Exclusionary Safety Values of Potential Clinical Concern

Hematology	
Leukocytes	<2 or >17.5 x 10 ³ /mm ³
Platelets	<75 or >700 x 10 ³ /mm ³
Comprehensive Metabolic Panel	

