Nitroprusside infusion has been widely used for decades to control profound hypertension and most recent reviews have concluded that it is quite safe at doses less than 2 $\mu\text{g}/\text{kg}/\text{min}$. The most important adverse reactions to sodium nitroprusside are the avoidable ones of excessive hypotension and cyanide toxicity. (Package Insert <http://medlibrary.org/lib/rx/meds/nitropress/> - last revised January 16, 2014).

No adverse effects were observed in 10 schizophrenia subjects who received nitroprusside 0.5 $\mu\text{g}/\text{kg}/\text{min}$ in the study by Hallak et al., including no cases of hypotension despite administering nitroprusside to two subjects treated with chlorpromazine (500 mg/d and 300 mg/d); chlorpromazine has the greatest propensity for orthostatic hypotension of any antipsychotic and subjects taking this drug will be excluded from the study. Nitroprusside was also added to high-dose ziprasidone (240 mg/d) and high dose risperidone (8 mg/d) without measurable effects on blood pressure or EKG.

The potential for cyanide toxicity is greatest when more than 500 $\mu\text{g}/\text{kg}$ of sodium nitroprusside is administered faster than 2 $\mu\text{g}/\text{kg}/\text{min}$, as cyanide is generated faster than the unaided patient can eliminate it. Cyanide toxicity will be avoided in this study as the dose administered is very low, and individuals with renal disease will be excluded. Also, the study treatment will be infused within 3 hours of preparation as sodium nitroprusside is stable in solution for 24 hours.

Subjects will be continuously monitored for adverse effects during the infusion and blood pressure and heart rate will be taken and recorded 2 hours post infusion.

Given that subjects with renal disease, a history of orthostatic hypotension or medications that destabilize blood pressure will be excluded from the study, and that the infusion rate of SNP for subjects randomized to active drug in this study will be very low (0.5 $\mu\text{g}/\text{kg}/\text{min}$), the risk of excessive hypotension and cyanide toxicity is very low.

H. STUDY ASSESSMENTS – PLAN AND METHODS

Study Conduct

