Given that subjects with renal disease, cardiac disease, hypotension or medications that destabilize blood pressure will be excluded from the study, and that the infusion rate of SNP for subjects randomized to active drug in this study will be low (0.5 $\mu\text{g}/\text{kg}/\text{min}$), the risk of excessive hypotension and cyanide toxicity is low.

Sodium nitroprusside does have some potential for drug-drug interactions. The hypotensive effect of sodium nitroprusside is augmented by that of most other hypotensive drugs, including ganglionic blocking agents, negative inotropic agents, and inhaled anesthetics. Subjects taking any of these drugs will be excluded from the study. Patients will also be advised not to take these medications during the course of the study.

Infusion Monitoring and Discharge Procedures

The study treatment will be infused with a volumetric infusion pump and the blood pressure of a subject will be continuously monitored by a cardiologist, anesthesiologist, or medically qualified designate as per institutional guidelines. A study physician will be available for consultation on any participant safety issues that arise during the infusion. Each participant will be allowed to rest in a semi-recumbent position. Each subject will receive an intravenous line. The study treatment will be infused with a volumetric infusion pump and the blood pressure of a subject will be continuously monitored by a cardiologist, anesthesiologist, or medically qualified designate as per institutional guidelines. To maintain the double blind, each subject will receive an infusion for 4 hours. Nitroprusside or placebo will be administered at the dose specified in the randomization scheme. Subjects will have one-to-one nursing care during the infusion of the study treatment.

The assigned nurse or medically qualified designate will perform the following monitoring procedures, as developed by the consulting cardiologist:

- Pre-Infusion: 12-Lead ECG (Time -1 to Time 0, baseline)
- During Infusion:
 - 12-Lead ECG @ 30 min
- Post-Infusion:
 - 12-Lead ECG @ 60 min post-infusion
- Vital Signs: BP, HR and O2 sat (same arm, non-IV arm)
Pre-Infusion (baseline)
During Infusion:
 - Q5 min Xs 30 minutes then Q10 min Xs 3.5 Hrs (210 min)
- Post-Infusion:
 - Q5 min Xs 30 minutes then Q10 min Xs 1.5 Hrs (90 min)

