The hypotensive effect of sodium nitroprusside is augmented by that of most other hypotensive drugs, including ganglionic blocking agents, negative inotropic agents, and inhaled anesthetics. Subjects taking any of these drugs will be excluded from the study.

Concomitant Therapy

The subject may not have adjustment of psychotropic medications except for benzodiazepines or anticholinergic agents if deemed absolutely necessary by the Investigator for relief of transient symptoms. (See Appendix 3: Medications Allowed and Not Allowed as Concomitant Medications). Subjects must be questioned at each study visit concerning any new medications or changes in current medications including over-the-counter medication and topical medication. All medications and therapies administered or taken by the subject beginning 30 days prior to signing the ICF and throughout the study will be recorded. The subjects' antipsychotic medication type should have remained unchanged for at least eight (8) weeks prior to screening into the study, at constant dose for at least 4 weeks, and should be expected to remain unchanged during the study.

For each medication and non-study treatment, the following will be documented:

- Medication/treatment name (generic name may be used if trade name is unknown)
- If an anti-psychotic medication, whether typical or atypical.
- Dose, unit, and frequency of dosing (individual dosages, not total daily dose). Note: Each new dose of medication should be recorded as a separate entry, with the exception of medications that are given on a sliding scale. For these, it is acceptable to enter the range of the dosage, including the start and stop dates for which the specified dosage range was used.
- Route of dosing
- Indication for use
- The start date
- The stop date (if medication/therapy is not ongoing)

Discontinuation from Study Treatment

Every effort will be made to keep the patient in the study for the full study period consisting of two phases of treatment with follow-up assessments. Acceptable reasons for early discontinuation include the following: 1) request of patient, 2) decision of physician, 3) serious adverse event, and 4) protocol violation.

Medical Reasons for Discontinuation:

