APPENDIX 3: CONCOMITANT MEDICATIONS ALLOWED

Drug Name or Class	Episodic Use (prn)	Chronic Use	Restrictions/Comment
Analgesics	Y	Y	Non-narcotic analgesics are allowed. Medically appropriate episodic use of narcotic analgesics is allowed for acute medical indications but is limited to no more than 3 days for each episode. Chronic NSAID use is allowed; tramadol is not allowed.
Anesthetics, general	Y	—	If procedures requiring general anesthesia are to occur/have occurred, please contact MGH CTNI to report the medical condition(s).
Anesthetics, local	Y	N	—
Anorexics	N	N	—
Antacids	Y	Y	—
Antiacne	Y	Y	Topical agents only, including topical antibiotics. Isotretinoin (Accutane) is not allowed.
Antiangular agents	N	N	—
Antiarrhythmics	N	N	—
Antiasthma agents	Y	Y	—
Antibiotics	Y	Y	Chronic use of topical or oral antibiotics for acne is allowed, with the exception of the MAOI linezolid (Zyvox) and isoniazid, which are not allowed. Erythromycin, clarithromycin, rifampin are excluded.
Anticoagulants	N	N	Warfarin (Coumadin) is not allowed. Antiplatelet agents are allowed (see "Antiplatelets").
Anticholinergics	Y	Y	Except for scopolamine.
Anticonvulsants	N	YY	Gabapentin and pregabalin are allowed. Other anticonvulsants are not allowed, including lamotrigine and carbamazepine.
Antidepressants	N	Y	Stable (for at least 4 weeks prior to screening), ongoing antidepressant therapy is required during the course of the study. No dose changes are allowed during the study. Monoamine oxidase inhibitors (which may have unknown drug-drug interactions) are excluded. Concomitant use of trazodone (up to 200mg daily) is allowed. Nefazodone is excluded.

Antidiarrheal preparations	Y	N	Only loperamide HCl (Imodium), bismuth subsalicylate (Pepto-Bismol), and kaolin preparations are allowed.
Antifungals, systemic	N	Y	—
Antifungals, topical	Y	Y	Ketoconazole and itraconazole are excluded
Antihistamines	Y	Y	The use of combinations containing pseudoephedrine or phenylephrine is not allowed. Combination products containing the word nighttime or some synonym routinely include a sedating antihistamine and are not allowed. Combination products ending in “-D” routinely contain a stimulant such as phenylephrine, and the appropriate limits above apply to them.
Anti-hypertensives	N	Y	Diltiazem, verapamil are excluded
Anti-impotence medications	N	N	—
Anti-inflammatory drugs	Y	Y ^a	Indomethacin (Indocin) and systemic corticosteroids are not allowed.
Antifungal	Y	Y	Itraconazole is excluded

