Antimigraine	Y	Y	Triptans are not allowed
Antinauseants/Antiemetics	Y	N	Phosphoric acid preparations (Emetrol, Emecheck), bismuth subsalicylate (Pepto-Bismol), cola syrup, 5-HT ₃ receptor antagonists (e.g., ondansetron), and prokinetic agents (metoclopramide) are allowed. Scopolamine is not allowed (see section on antihistamines).
Antineoplastics/Immunosuppressant agents	N	Y ^c	Interferons, methotrexate, and other immunosuppressant agents are not allowed. Call MGH CTNI for approval for certain cases in cancer remission maintaining therapy.
Antiobesity/Appetite suppressants	N	N	OTC Alli (Xenical), sibutramine (Meridia), and phentermine (Adipex-P and others) are not allowed.
Antiplatelet agents	N	Y ^b	Aspirin (maximum 325 mg/day) and clopidogrel (Plavix) are allowed.
Antipsoriatic treatments	Y	Y	Only topical agents are allowed. Acitretin (Soriatane) is not allowed.
Antipsychotics	N	Y	Stable in dosing at least 8 weeks prior to randomization is allowed.

Antismoking medications	N	Y ^c	Varenicline (Chantix) is not allowed. Chronic nicotine replacement may be allowed in certain cases after review with MGH CTNI.
Antiviral agents	Y	Y	Only oral or topical agents are allowed. Only acyclovir, famciclovir, valacyclovir, penciclovir, docosanol, trifluridine, and vidarabine are allowed. Amantadine, rimantadine, indinavir, nelfinavir, ritonavir, saquinavir are not allowed. Tamiflu (oseltamivir phosphate), and Relenza (zanamivir) inhalants are permitted for influenza prophylaxis but use is limited to a 7- to 14-day course in accordance with prescribing information. Interferons are not allowed.
Anxiolytics	Y	Y	Chronic, stable treatment with benzodiazepines for reasons other than sleep is allowed. Stable dosing at least four weeks prior to randomization is required for sleep agents. Up to 1mg of benzodiazepine in a 24h period can be utilized as needed during the study period.
Benign prostatic hyperplasia treatments	N	Y ^b	Male patients who have symptoms of obstructed voiding should not be included in the study. Surgically or medically treated patients must be asymptomatic and receiving a stable dosage of allowed medications (α -1 blockers, finasteride, or dutasteride) for 1 month before screening.
Buspirone	N	Y	Stable in dosing at least four weeks prior to randomization is allowed.

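### The safety text says subjects on hypotensive drugs are excluded, but no numbered criterion excludes them as a class and Appendix 3 allows several; the CNS-drug lists and the suicide look-back also disagree

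*Protocol*

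**What the plan says.** Protocol Section H (Safety Profile of Sodium Nitroprusside) and Section I (Possible Drug Interactions) carry the same warning: "The hypotensive effect of sodium nitroprusside is augmented by that of most other hypotensive drugs", followed by "including ganglionic blocking agents, negative inotropic agents, and inhaled anesthetics. Subjects taking any of these drugs will be excluded from the study". Section H adds: "Patients will also be advised not to take these medications during the course of the study".

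Two risk statements build on this. The Rationale for the Inclusion/Exclusion Criteria in Section G counts, among its reasons for a very low hypotension risk, that "medications that destabilize blood pressure will be excluded from the study". Section H makes a similar argument, listing "renal disease, cardiac disease, hypotension or medications that destabilize blood pressure will be excluded from the study".

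The enrolment rules read differently:

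- **Exclusion 4** (synopsis and Section G) bars chlorpromazine, PDE-5 inhibitors, nitrates (nitrites in Section G) and CNS-active drugs. Besides antipsychotics other than chlorpromazine, the exceptions are "anticholinergics, b-adrenergic antagonists, amantadine, biperiden, diphenhydramine, lorazepam, zolpidem, and temazepam".
- **Appendix 3, anti-hypertensives:** chronic use is allowed, with one restriction: "Diltiazem, verapamil are excluded".
- **Appendix 3, prostatic hyperplasia treatments:** alpha-1 blockers are among the permitted drugs for patients "receiving a stable dosage of allowed medications".
- **Appendix 3, diuretics:** chronic use is allowed at a stable dose.

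Separately, the synopsis excludes a significant suicide attempt in the past 12 months. Section G, Exclusion 9, uses 6 months.

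**The concern.** The safety argument counts on a drug exclusion that the numbered criteria do not contain. A site working from Section G and Appendix 3 could enrol a patient on a beta-blocker or another anti-hypertensive into a vasodilator infusion study, while the safety text tells the IRB and investigators that such patients are kept out. Excessive hypotension is one of the two adverse reactions that the protocol itself calls most important and avoidable.

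The two CNS-drug lists and the two look-back periods raise a lesser problem of the same kind. With about four sites, the same patient could be judged eligible at one and ineligible at another, depending on which page is followed.

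**Working it through.** No figure in the plan bears on this point, so the check is a comparison of texts.

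**Blood-pressure drugs.** The exclusion can be read narrowly (only the three classes named in Sections H and I) or broadly (most other hypotensive drugs, or anything that destabilises blood pressure).

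| Drug class | Narrow reading | Broad reading | Exclusion 4 | Appendix 3 |
|---|---|---|---|---|
| Beta-blockers | Excluded, if negative inotropes | Excluded | Exempt from the CNS-drug ban | Chronic use allowed when taken as an anti-hypertensive |
| Other anti-hypertensives, except diltiazem and verapamil | Not named | Excluded | Silent | Chronic use allowed, no stability condition |
| Alpha-1 blockers | Not named | Excluded | Silent | Allowed if stable |
| Diuretics | Not named | Excluded | Silent | Chronic use allowed if stable |

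Beta-blockers conflict on both readings. That they are negative inotropes is general pharmacology, taken here as an assumption; the protocol does not classify them. The other three classes conflict only on the broad reading. The anti-hypertensive row has no counterpart to footnote b, which the diuretic and prostate rows carry (taken for at least 3 months, dose stable for at least 1 month).

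What already narrows the gap:

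- Exclusion 1 removes renal insufficiency, heart failure, arrhythmia and past infarction. Exclusion 2 removes symptomatic orthostatic hypotension.
- Exclusion 4 names chlorpromazine, PDE-5 inhibitors and nitrates or nitrites.
- Appendix 3 bars antiarrhythmics, diltiazem and verapamil.
- Exclusions 3, 5 and 11 let the investigator, or the PI with the medical monitor, exclude further patients by judgement.

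None of these excludes, as a fixed rule, a patient whose only relevant feature is a beta-blocker or a permitted anti-hypertensive.

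**CNS drugs.** Exclusion 4 in Section G is a closed list. These Appendix 3 rows allow drugs outside it:

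1. antidepressants
2. anticonvulsants (gabapentin, pregabalin)
3. anxiolytics (benzodiazepines generally)
4. buspirone
5. dopaminergics
6. lithium
7. sedatives/hypnotics (zaleplon, benzodiazepine hypnotics, low-dose trazodone)

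Seven is a minimum, since the analgesics row also allows short courses of narcotics. In the other direction, the antiviral row bars amantadine, which Exclusion 4 exempts. The synopsis and Section I (Concomitant Therapy) refer the reader to Appendix 3; Exclusion 4 in Section G does not.

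**Suicide look-back.** 12 − 6 = 6 months' difference. The C-SSRS baseline window in Section H is six months. The medical history in Section H records suicidality with dates, so a source exists for months 7 to 12.

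**Analysis.** The ITT population is all randomised subjects, and none of the sample-size inputs (differences of 9 and 11 points, SD 14, 20% attrition, 30% placebo response) depends on these drugs. Per Protocol membership could be affected: Table 3 makes enrolling an ineligible subject without a protocol exception a major violation, and major violations remove a subject from that supportive population.

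**The case against.** The best defence has four parts.

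- **Exclusion 4 does not admit anyone.** It exempts beta-blockers from its own ban only. Exclusions are cumulative, and Sections H and I are current protocol text. This is correct, so a reader who infers that Exclusion 4 grants entry to beta-blocker users goes too far. What stands is that no other numbered criterion bars them and that Appendix 3 allows chronic anti-hypertensives, so a site has good reason to read them as permitted.
- **Only three classes are named.** On that reading, most anti-hypertensives, alpha-1 blockers and diuretics do not conflict with Sections H and I. This stands, and it is why the conflict is graded. The separate statements about drugs that destabilise blood pressure still sit badly with the Appendix 3 rows.
- **Patients are protected anyway.** Everyone gets a low rate (0.5 µg/kg/min), a 10-minute half-rate run-in, blood pressure every 5 to 10 minutes, one-to-one nursing and stop rules, and some criteria are discretionary. These are real safeguards. They respond to hypotension or depend on judgement, and neither delivers an exclusion stated as certain.
- **The CNS lists are linked.** The synopsis points to Appendix 3, and the amantadine bar may apply only to antiviral use. Both are fair, but Section G lacks the pointer and the lists still differ.

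A reader might also infer that an enrolled patient would be told to stop a chronic drug that Appendix 3 allows. The advice sentence directly follows the exclusion sentence and reads more naturally as telling enrolled subjects not to start such drugs.

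**Conclusion.** The inconsistency is real and should be fixed. The stated exclusion, which supports the low-risk statements in Sections G and H, is not carried into the numbered criteria, and Appendix 3 contradicts it in part.

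The conflict is clearest for beta-blockers, assuming they count as negative inotropes. For other anti-hypertensives, alpha-1 blockers and diuretics it depends on the broader wording. The documents do not say how many patients take these drugs, so the number affected cannot be given.

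The secondary conflicts are at least seven Appendix 3 rows looser than Exclusion 4, one row stricter, and a look-back of 12 against 6 months.

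This is a matter of safety and eligibility consistency. The documents do not support an inference that it undermines the ITT analysis, sample size or power. Nor do they show that 6 months is the right look-back: the six-month C-SSRS window does not settle it, because the medical history covers the longer period.

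**What to change.** **Blood-pressure drugs, one of two routes:**

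1. Add a numbered exclusion that matches Sections H and I, and bring the beta-blocker exemption in Exclusion 4 (synopsis and Section G) and the blood-pressure rows of Appendix 3 into line with it.
2. If the clinical team wants to keep these drugs, correct the exclusion and low-risk statements in Sections G, H and I, and give the anti-hypertensive row a stability condition like footnote b.

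**CNS drugs:** make Exclusion 4 and Appendix 3 one list, settle amantadine, and add the Appendix 3 cross-reference to Exclusion 4 in Section G.

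**Suicide look-back:** use one value in the synopsis and Section G, chosen by the clinical team. If 12 months is kept, name the medical history as the source beyond the six-month C-SSRS window.

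**Cost:** a wording amendment. The first route narrows eligibility slightly and may slow recruitment a little. Neither route changes the sample size or the primary analysis.
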